*** Administration and Dosing of Etelcalcetide and Management of Hypocalcemia and Over-suppression of PTH**

The protocol will allow for changes in the dose of etelcalcetide, vitamin D sterols, calcium supplements and phosphate binders based on the levels of serum PTH, calcium and phosphorus that are obtained on a monthly basis as part of the standard of care monthly lab set for patients on hemodialysis.

- 1) Administration: by intravenous bolus injection into the venous line of the dialysis circuit at the end of hemodialysis treatment during rinse back or intravenously after rinse back.
- 2) Initiation and dose adjustment of etelcalcetide
 - a) Starting dose of etelcalcetide: 5.0 mg
 - b) Maximum dose of etelcalcetide: 15.0 mg
 - c) Dose adjustments: increase in 2.5-5.0 mg increments at weeks 4, 8, 12 during the titration phase and at the time of the monthly lab sets during the treatment phase based on PTH and calcium.
- 3) Missed doses
 - a) If a regularly scheduled hemodialysis treatment is missed, do not administer any missed doses.
 - i) Resume etelcalcetide at the end of the next hemodialysis treatment at the prescribed dose.
 - ii) If doses of etelcalcetide are missed for more than 2 weeks, re-initiate etelcalcetide at the recommended starting dose of 5 mg (or 2.5 mg if that was the patient's last dose).
- 4) Management of hypocalcemia
 - a) Monitor corrected serum calcium one-week after starting or changing a dose of etelcalcetide
 - b) Drop in corrected serum calcium WNL of the reference range
 - i) no dose change
 - c) Drop in serum calcium < LLN of the reference range but ≥ 7.5 mg/dL without symptoms of hypocalcemia
 - i) increase calcium in dialysate to the next highest level and/or start calcium oral supplement and monitor as per HD unit safety protocol
 - (1) If calcium has normalized and PTH remains within the target range: no dose change
 - (2) If calcium has normalized but PTH has risen above the target range: increase dose by 2.5 mg and monitor PTH and calcium per HD unit safety policy
 - (a) If calcium and PTH are at goal: no dose change
 - (b) If calcium < LLN but ≥ 7.5 mg/d without symptoms: increase calcium in dialysate and/or start calcium oral supplement and monitor as per HD unit safety protocol
 - (i) If calcium remains < LLN but ≥ 7.5 mg/d, changes in levels of active vitamin D sterols can be implemented
 1. Decreasing the dose of etelcalcetide can be implemented after the above steps have been undertaken. The dose should be lowered in 2.5 mg increments and monitoring of PTH and calcium should be obtained within a week of any changes.
 - d) Drop in serum calcium < 7.5 mg/dL or below the reference range with symptoms of hypocalcemia
 - i) Hold drug and monitor as per HD unit safety protocol
 - (1) If repeat calcium level WNL: restart dose at 2.5-5.0 mg lower than the previous dose and monitor as per HD unit safety protocol
 - (a) If repeat calcium level remains WNL and PTH at goal: no dose change
 - (b) If repeat calcium level remains WNL and PTH above goal: increase dose by 2.5 mg and monitor per HD unit safety protocol
 - (i) If calcium level < LLN but ≥ 7.5 mg/d without symptoms: follow algorithm 4c
 - (ii) If calcium level < 7.5 mg/dL or below the reference range with symptoms of hypocalcemia: proceed as per 4di
 - 5) Management of excessive suppression of PTH below the KDIGO target (< 2x LLN)

- i) Measure PTH after 4 weeks from initiation or dose adjustment
- ii) Without hypocalcemia: decrease dose by 2.5-5.0 mg and monitor as per HD unit safety protocol
- iii) With hypocalcemia: as per (4) above

Sample Size for Aim 1. N = 20

Sample Size Justification for Aim 1. The proposed sample size of 20 participants provides 80% power and 5% alpha for a two-tailed dependent T-test of the within-subject difference in the pre- and post-treatment hardness measured by Ramen/nanoindentation in the formation regions of 0.91-SDs. While we expect moderate variability in hardness between subjects, the within subject change due to treatment sought here is expected to be relatively similar across subjects given the established efficacy of etelcalcetide on other outcomes¹³. Behets et al¹⁴ reports patients with end stage renal disease show a baseline bone formation rate of 799 ± 334 (mean \pm SD), a O.Pm/B.Pm(%) of 18.9 ± 9.4 and a E.Pm/B.Pm of 13.1 ± 4.3 which assures a measurable region for the Ramen/nanoindentation assessment of hardness.

Sample Size for Aim 2. N = 35 (20 from Aim 1 plus 15 additional patients)

Sample Size Justification for Aim 2. The proposed sample size of 35 participants provides >80% power and 5% alpha to detect a change in femoral neck BMD of 0.5% f and a 0.5 standard deviation change in radius failure load by HR-pQCT from pre-treatment to the 6-month endpoint. For femoral neck BMD by measured by DXA, Lien et al¹⁵ reported that in 8 patients with CKD treated with cinacalcet for 6 months, areal BMD at the femoral neck increased $2.2 \pm 1.1\%$ ($p < 0.05$). For failure load outcomes, in a longitudinal study of 29 patients with ESKD who underwent kidney transplantation, we reported that failure load decreased by $3.5 \pm 7.0\%$ ($p=0.0081$) over 12-months¹⁶; our larger sample size will permit detection of at least a 3.4% change in radius failure load due to suppression of PTH production by etelcalcetide.

Sample Size for Aim 3: N = 35 (20 from Aim 1 plus 15 additional patients)

Sample Size Justification for Aim 3: The proposed sample size of 35 participants provides >80% power and 5% alpha two-tailed dependent T-test of the change in T50 from baseline to the 6-month endpoint. Based on Smith et al¹⁰, each standard deviation (SD) decrease in T50 was associated with a 39% increase in odds of all-cause mortality. Assuming that the variability in T50 in patients on hemodialysis patients enrolled into this prospective cohort study are similar to those reported in Smith et al¹⁰, approximately 20 patients would be required to detect a 1-SD decrease in T50. Our sample size of 35 patients will permit the detection of a 0.7-SDs decline in T50. We assume that a reduction of lesser magnitude is of unclear clinical significance

Protection of Human Subjects

This study qualifies as clinical research and will be conducted in compliance with GCP and all regulatory requirements for the protection of human subjects.

Informed Consent

Informed consent will be obtained from all participants. The purpose of the study will be explained to patients prior to recruitment as part of the informed consent procedures, which is defined as “to evaluate the effects of etelcalcetide on bone quality and the tendency of your soft tissue to calcify”. The study methods, namely the assessment of physical exam and medical history; the evaluation by imaging modalities; the collection of blood; and bone biopsy will be described. The fact that the informed consent and the study protocol have been approved by the IRB will be emphasized. The potential risks and direct benefits to the patient will be explained. The potential benefit from this study to future patients will be explained. The fact that the patient has the option not to participate and will receive the same standard medical care regardless of participation will be emphasized. The rights of the patient, including the voluntary nature of participation and the right to withdraw the consent at any time, will be explained. We will also explain that this research does not affect the clinical management of the patient as determined by their nephrologist. In addition, patients will be informed that by enrolling they will have more intensive monitoring of bone health than they would if they do not participate. Thus, participating in this study should not put the subject at any risk for altering management deemed appropriate by the patient's nephrologist. The methods in place for maintaining patient confidentiality will be explained. This will include registering all data under a subject specific alpha-numeric system, storing all records in password protected and encrypted files. A copy of the signed informed consent will be placed in the patient's permanent medical record, a second copy of all consents will accompany the data to be kept in the PI's office, and a third copy will be provided to the participant.

Potential Risks

All key personnel involved in the design or conduct of research involving human subjects will have received the required education on the protection of human research participants prior to funding of this project.

The potential risks are related to hypocalcemia, loss of confidentiality, radiation exposure from DXA for measurement of bone density and HR-pQCT for measurement of volumetric density and microarchitectural parameters and the bone biopsy procedure. All blood will be obtained from the dialysis line to avoid venipuncture.

- **Hypocalcemia.** Etelcalcetide has been associated with a decrease in serum calcium. We will monitor for and minimize this risk as described in the main protocol.
- **Loss of confidentiality.** due to breaches in data security or deductive disclosure. To ensure that participants' confidentiality is not compromised, we will minimize these risks through the procedures discussed below.
- **Radiation.** The total expected radiation dose for the entire study is approximately 8 mrem (80 μ Sv) for 2-sets of DXA and HR-pQCT scans obtained at the baseline and 12-month visits. This compares to 2400 μ Sv natural background in a year, 8000 μ Sv for a standard chest CT, 450 μ Sv for a mammogram, and 60 μ Sv for a round-trip transcontinental plane flight. The total radiation exposure for the study will be below the maximal acceptable dose.
 - a) **CUMC DXA (2 sets of scans).** Radiation exposure for DXA (spine, one hip, forearm) using the Hologic QDR4500 (fast scan) is 10.85 μ Sv (21.68 μ Sv for 2 sets of scans).
 - b) **HR-pQCT (one forearm and one leg; 3 sites each).** 30 μ Sv (60 μ Sv for 2 sets of scans)
- **Transiliac crest bone biopsy.** The risks of the bone biopsy include those related to tetracycline and demeclocycline administered in advance of the biopsy to label sites of bone formation, the risks of conscious sedation, and the risks of the biopsy itself. Tetracycline-type agents may cause stomach upset and skin rashes when subjects taking them are exposed to sunlight. Subjects will be counseled to discontinue tetracycline/demeclocycline if gastrointestinal symptoms develop and to avoid sunlight exposure during the 6 days they are taking the medication. Conscious sedation will be offered to subjects in order to minimize anxiety, provide pain relief, and diminish recall. Patients receiving conscious sedation may have brief, transient loss of protective reflexes. Either IV or PO sedation will be provided with a combination of a benzodiazepine (e.g, midazolam, valium) and a narcotic-based pain medication (e.g., fentanyl, oxycodone). Risks will be minimized by complying with all procedures as required by CUMC's Policies and Procedures Manual. Specifically, all nurses and physicians involved in performing bone biopsies will have certification in Advanced Cardiac Life Support, the procedure will be conducted in the Biopsy Suite in the Division of

Nephrology at CUMC, and vital signs (including O₂ saturation) will be monitored at regular intervals during and after the procedure. An M.D. or Nurse-anesthetist will be present to administer the conscious sedation. Complications from the biopsy are very unusual. Occasionally there will be a bruise at the site or discomfort at the biopsy site that persists for a few days.

Protection against risk

The risks of DXA, HR-pQCT, bone biopsy and loss of confidentiality are described above. Provision for medical treatment, should it be required, will be included in the written informed consent; each subject will receive a copy. Confidentiality of patient data will be ensured. No patient will be identifiable in any publications resulting from this study. Patients are identified by code rather than name in the database. Access to the computer data bank is limited by password protection.

- **Hypocalcemia.** We have implemented a protocol to monitor and manage hypocalcemia.
- **Radiation.** DXA, and HR-pQCT have the risk of radiation exposure. The amount of radiation that participants will receive as a result of participation in the study will be discussed with each participant in detail as part of informed consent procedures. Females will undergo a urine pregnancy test prior to the DXA and HR-pQCT. Pregnant females will be excluded from the study at any time point in order to protect the unborn fetus.
- **Bone biopsy.** The risks of bone biopsy will be included in informed consent procedures. Furthermore, our use of a quadruple label method negates the need for 2 bone biopsy procedures.
- **Confidentiality.** Only investigators and the study research staff will have access to the data. All data are recorded with linkages to subject identities to be able to track changes over their longitudinal participation in the study. A data collection/tracking system developed for use in previous studies is used in this research, and will ensure confidentiality for all participants. All collected data will be identified by study identification numbers but not names. Only the study investigators will have access to a master list with the study identification numbers and names. The master list will be kept on a secure server on a research shared access network. All data containing PHI will be stored on password-protected encrypted CUMC computer or the secure research servers. Computers are password protected, encrypted and regularly backed-up to prevent data loss. Paper documents, such as consent forms, will be stored in locked cabinets in areas of restricted access. Only the research staff will have access to this information, unless written permission is received from the participant. The data collected as part of this study will be retained indefinitely. All data and records generated during this study will be kept confidential in accordance with Institutional policies and HIPAA on subject privacy, and the investigators and other site personnel will not use such data and records for any purpose other than conducting the study.

Safety Reporting

The Principal Investigator will be responsible for patient safety. As this is not a clinical trial, there is minimal potential for injury.

Adverse events will be monitored throughout the study and reported to Amgen as follows:

- Suspected Unexpected Serious Adverse Reaction (SUSARs) will be submitted at the time of regulatory submission
- Pregnancy/Lactation Reports will be submitted within 10 calendar days of Sponsor awareness
- Applicable Annual Safety Reports will be submitted annually
- Other Aggregate Analyses (any report containing safety data generated during the course of the study) will be submitted at the time of ISS Sponsor submission to the IRB (or other body governing research conduct)
- The Final (End of Study) Report will be submitted to Amgen at the time of ISS Sponsor submission to the IRB (or other body governing research conduct), but not later than 1 calendar year of study completion

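### With PTH below the KDIGO range, mild asymptomatic hypocalcemia is the only calcium band whose first printed step neither lowers nor holds etelcalcetide

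*Combined protocol and SAP*

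**What the plan says.** The rules are in the section on administration and dosing of etelcalcetide and management of hypocalcemia and over-suppression of PTH.

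**Item 5, PTH below the KDIGO range.**
- 5(i): "Measure PTH after 4 weeks from initiation or dose adjustment".
- 5(ii): "Without hypocalcemia: decrease dose by 2.5-5.0 mg and monitor as per HD unit safety protocol".
- 5(iii): "With hypocalcemia: as per (4) above".

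**Item 4, hypocalcemia.**
- 4(a) checks corrected calcium one week after a start or dose change.
- 4(c) covers calcium below LLN but at least 7.5 mg/dL without symptoms. Its first step is to "increase calcium in dialysate to the next highest level and/or start calcium oral supplement and monitor as per HD unit safety protocol". Its PTH branches are "If calcium has normalized and PTH remains within the target range: no dose change", "If calcium has normalized but PTH has risen above the target range: increase dose by 2.5 mg" and, after that increase, "If calcium and PTH are at goal: no dose change". If calcium stays low after the increase, "changes in levels of active vitamin D sterols can be implemented". A dose decrease in 2.5 mg increments is then permitted once those steps have been taken.
- 4(d) covers calcium below 7.5 mg/dL, or below range with symptoms. The drug is held and, once calcium is normal, restarted 2.5-5.0 mg lower.

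**The concern.** The Potential Risks section links etelcalcetide to falling serum calcium. A patient with over-suppressed PTH and mildly low calcium therefore shows two signs that fit too much drug. A patient with over-suppressed PTH and normal calcium shows one. Followed as printed, the rules cut the dose first for the second patient but not for the first.

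Treating calcium first is sensible when PTH is in or above target, because it preserves PTH control. That reason is absent when PTH is already below the KDIGO range, and the protocol gives no other reason for carrying the sequence over. Raising calcium supply alone also leaves the over-suppression, which item 5 exists to manage, without a dose response.

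The stake is patient safety and adherence to the PTH target of 300-400 pg/mL on which all three aims rest. The protocol relies on this algorithm as its safeguard against hypocalcemia.

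**Working it through.** There is no stated figure to reproduce. The check fixes PTH below the KDIGO range and follows the printed rules.

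**Step 1. First printed step in each calcium band.** The three bands cover all calcium values.

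| Band | Calcium | Route | First step on etelcalcetide |
|---|---|---|---|
| A | Not low | 5(ii) | Decrease 2.5-5.0 mg |
| B | Below LLN, at least 7.5 mg/dL, no symptoms | 5(iii) to 4(c)(i) | None stated; calcium measures only |
| C | Below 7.5 mg/dL, or below range with symptoms | 5(iii) to 4(d)(i) | Hold, later restart 2.5-5.0 mg lower |

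Two of three bands begin with a decrease or hold; band B has neither. Item 4(b) leaves the dose alone when calcium drops but stays within normal limits. That is not hypocalcemia, so with low PTH the specific rule 5(ii) governs and band A stands.

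**Step 2. Can item 4 supply the missing action?** Its PTH-dependent branches are:

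| Branch | Calcium | PTH | Dose |
|---|---|---|---|
| 4(c)(i)(1) | Normalized | In target | No change |
| 4(c)(i)(2) | Normalized | Above target | Increase 2.5 mg |
| 4(c)(i)(2)(a) | At goal | At goal | No change |
| 4(d)(i)(1)(a) | Normal | At goal | No change |
| 4(d)(i)(1)(b) | Normal | Above goal | Increase 2.5 mg |

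Total 5 = 3 no change + 2 increase + 0 for low PTH. Within 4(c) alone, 3 = 2 + 1 + 0. All five require calcium to be normal or at goal, so none describes a patient still in band B.

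**Step 3. Does silence mean keep the dose?** No. An explicit instruction not to change the dose appears four times in item 4, at 4(b)(i), 4(c)(i)(1), 4(c)(i)(2)(a) and 4(d)(i)(1)(a). It does not appear at 4(c)(i). Band B is a gap, not an order to continue.

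**Step 4. The one decrease in 4(c).** By its numbering it sits under 4(c)(i)(2)(b), a branch reached only after PTH has risen above target and the dose has been raised. A low-PTH patient would not arrive there. It can also be read as the last step of all of 4(c). On either reading it is optional and follows the calcium and vitamin D steps. If calcium normalizes while PTH stays low, 5(ii) then applies. The gap therefore lasts as long as calcium stays in the mild band.

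**Step 5. Where the threshold lies.** Inclusion criterion 6 gives 9 x ULN as 720 pg/mL at this site.
- ULN = 720 / 9 = 80 pg/mL
- KDIGO floor = 2 x 80 = 160 pg/mL
- Distance to the lower end of the target = 300 - 160 = 140 pg/mL

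The heading of item 5 prints the threshold as twice the LLN. I read it as twice the ULN, the KDIGO floor given in the Background and in exclusion criterion 3. Steps 1 to 4 hold with either threshold.

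**The case against.** The strongest case is that this is a drafting matter with little clinical effect.

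- **Discretion.** The dosing section opens by allowing dose changes on monthly labs. The Informed Consent section says the research does not alter the nephrologist's management, and Safety Reporting treats these rules as guidelines for recommendations. Nothing in 4(c) forbids an immediate decrease. This stands and limits the harm. It is not a complete answer: inclusion criterion 12 requires the physician to accept the protocol's dosing, and discretion does not mend a cross-reference to a rule with no low-PTH branch.
- **Timing.** Calcium is read at one week and PTH at four. A patient found in band B at week 1 may have had up to three weeks of 4(c) measures before low PTH is known. The optional decrease may by then be open on the wider reading of 4(c). This also stands: for such patients the added delay may be small or nil. It does not help a patient whose mild hypocalcemia and low PTH are found together.
- **Branch counts.** Item 4 manages calcium, and low PTH with normal calcium belongs to 5(ii), so low-PTH versions of those branches would largely duplicate it. Fair, but 5(iii) hands the low-PTH, low-calcium patient to item 4, so its lack of a low-PTH branch matters.
- **Graded choice.** Calcium-first may be deliberate for mild hypocalcemia, and 4(c) uses 2.5 mg increments where the proposed step allows up to 5.0 mg. The sequence is reasonable for PTH in or above target. The 5(ii) range still lets the physician choose 2.5 mg.
- **Unseen source.** Monitoring is deferred to a dialysis-unit safety protocol that is not in the documents and might narrow the gap. That cannot be checked.

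**Conclusion.** The concern holds. With PTH below the KDIGO range, two of three calcium bands begin with a decrease or hold. The mild asymptomatic band begins with calcium measures alone, and its decrease is deferred until calcium normalizes or left optional after other steps. An over-suppressed patient with mildly low calcium is thus handled less protectively on paper than one with normal calcium.

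These are counts of rule branches, not of patients. The number affected, the length of any delay and any effect on endpoints cannot be quantified from the documents. No sample size or error rate is shown to depend on the gap. The 160 pg/mL figure assumes the ULN reading of item 5's heading; the conclusion does not. The point should be fixed because it concerns a safety rule and the remedy is cheap, not because a large effect has been shown.

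**What to change.** Reword 5(iii) only, for example:

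> *Calcium below LLN but at least 7.5 mg/dL, no symptoms: reduce etelcalcetide by 2.5-5.0 mg as in 5(ii), together with the calcium measures in 4(c)(i). Calcium below 7.5 mg/dL, or below LLN with symptoms: follow 4(d).*

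Leave 4(c) as it is for patients to whom item 5 does not apply. The step size is the one 5(ii) already uses for low PTH, and its lower end matches the 2.5 mg increment in 4(c).

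The cost is one line of protocol text, with no extra patients or study visits and no change for patients with PTH in or above target. Each decrease triggers the one-week calcium check that 4(a) already requires. The downside is that low-PTH patients in the mild band lose the calcium-first sequence, and their PTH may rise somewhat sooner from below the floor toward 300-400 pg/mL.

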with etelcalcetide improves bone hardness and mineralization using Ramen/nanoindentation and remodeling by histomorphometry using the quadruple label transiliac crest bone biopsy method in 20 ESKD patients with severe HPT.

Figure 2. Study timeline.

[figure not shown]

Table 1: Data Collection at each Study Visit

	Baseline	3 Months	9 Months
Informed consent	x		
Medical History	x		x
Physical Exam	x		x
Kt/V	x	x	x
Biomarkers of bone formation and resorption (BSAP, P1NP, CTX)	x	x	x

Procedures. This is a single-arm prospective cohort study to test the effects of 6-months of treatment with etelcalcetide on bone-tissue properties. We will obtain a single quadruple label bone biopsy to assess longitudinally the effects of 6-months of treatment with etelcalcetide on bone properties at the tissue level.

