Bone-tissue properties. We will use an integrated Raman/Nanoindentation system, which permits precise measurement of localized bone tissue properties (e.g., mineral/matrix, collagen) and indentation properties (e.g., hardness) within identical regions. Areas within the TCN and demeclocycline double label will be assessed for nanoindentation properties, and subsequently the same spatial location will be assessed for Raman-based measurements. Nanoindentation will occur using a Berkovich diamond indenter loading to a peak load of 10mN, a strain rate of 0.05 seconds and a holding period of 10 seconds. Oliver and Pharr methods will be used to determine the stiffness and hardness of the unloading curves. A total of 12-15 indentations will be performed within a given region. Following indentation, the same spatial regions will be assessed with Raman spectroscopy to determine the phosphate and matrix peaks after background and baseline shift correction. The ratio of phosphate:mineral will be calculated, along with other parameters (crystallinity and collagen crosslinking).

Hypothesis 2. Etelcalcetide will improve bone density, microarchitecture, and biomechanical competence in patients with ESKD.

Aim 2. To test if 6-months of treatment with etelcalcetide improves femoral neck areal BMD measured by DXA and failure load at the ultradistal radius measured by application of finite element analysis to HR-pQCT datasets. We will also quantify the effect of 6-months treatment with etelcalcetide on changes in areal BMD at the spine, total hip, and one-third and ultradistal radius measured by DXA, and cortical and trabecular volumetric BMD and microarchitecture, cortical porosity and tissue mineral density, and biomechanical competence at the ultradistal radius and tibia measured by HR-pQCT with application of finite element analysis.

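### Aim 1 does not define the SD behind its 0.91 SD hardness effect; on the SD-of-change scale that a paired t-test uses, 20 patients give 80% power for 0.66 SD

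*Combined protocol and SAP*

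**What the plan says.** Hardness is the primary endpoint of Aim 1, and the statistical methods plan a two-tailed dependent t-test of its change. The paragraph Sample Size Justification for Aim 1 says: "The proposed sample size of 20 participants provides 80% power and 5% alpha", and continues "for a two-tailed dependent T-test of the within-subject difference in the pre- and post-treatment hardness measured by Ramen/nanoindentation in the formation regions of 0.91-SDs".

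The next sentence expects moderate variability in hardness between patients, but says that "the within subject change due to treatment sought here is expected to be relatively similar across subjects". The documents give no SD of hardness, no SD of its change and no pre/post correlation.

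The Aim 1 procedures describe the design: "This is a single-arm prospective cohort study to test the effects of 6-months of treatment". There is therefore no second group to compare with.

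**The concern.** A power statement should be reproducible from its test, sample size, alpha and effect size. This one names all four, but the effect is in units of an SD that is not identified. The natural unit for a dependent t-test is the SD of the within-patient change, and on that scale 0.91 looks too large for 20 pairs at 80% power.

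What is at stake is how the primary result of the biopsy aim will be read. Someone who takes 0.91 SD at face value would treat a null result as uninformative about any smaller change. The figure also cannot be converted to hardness units, or adjusted for fewer evaluable biopsies, without knowing which SD it refers to.

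**Working it through.** **Inputs.** From the Aim 1 paragraph: n = 20, two-sided alpha 0.05, power 80%, dependent t-test, stated effect 0.91 SD. From the Aim 2 paragraph: N = 35, 0.5 SD, 3.4%, and a change in failure load of 3.5 ± 7.0%. The correlations r below are assumptions, since the documents give none.

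**1. Attempt to reproduce 0.91 with the stated test.** With d in SDs of the change, power is the probability that a noncentral t with n − 1 degrees of freedom and noncentrality d√n falls outside ±t(0.975, n − 1).

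- Solving for 80% power at n = 20 gives d = 0.6604.
- The stated value is 0.91 / 0.6604 = 1.378 times this, or 38% larger.
- At d = 0.91 the noncentrality is 0.91 × √20 = 4.07 and power is 97.1%.
- For d = 0.91, 11 pairs give 77.6% and 12 pairs give 81.8%.

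**2. Variants of the paired calculation at n = 20.** None of these gives 0.91:

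| Variant | Detectable SD of change |
|---|---|
| Normal approximation, 80% power | 0.626 |
| One-sided 5%, 80% power | 0.577 |
| Two-sided 5%, 90% power | 0.764 |
| Two-sided 5%, 95% power | 0.850 |

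Alpha of 0.005 comes close (0.912), but the paragraph states 5%.

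**3. Independent two-sample test.** With 20 per group, noncentrality d√(20/2) and 38 degrees of freedom, the 80%-power effect is 0.909, and power at 0.91 is 80.1%. This matches the stated figure but is not the planned test.

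**4. Between-patient SD.** With equal pre and post SDs, the SD of change is the SD of level × √(2(1 − r)). The detectable effect in SDs of level is then 0.6604 × √(2(1 − r)):

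| Assumed r | √(2(1 − r)) | 80%-power effect (SD of level) | Power at 0.91 |
|---|---|---|---|
| 0 | 1.414 | 0.934 | 77.9% |
| 0.2 | 1.265 | 0.835 | 86.2% |
| 0.5 | 1.000 | 0.660 | 97.1% |
| 0.8 | 0.632 | 0.418 | above 99.9% |

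The r that gives exactly 0.91 is 1 − (0.91 / 0.6604)² / 2 = 0.051.

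**5. Internal comparison with Aim 2.** That paragraph claims power above 80% for "a 0.5 standard deviation change in radius failure load by HR-pQCT from pre-treatment to the 6-month endpoint" and says the sample "will permit detection of at least a 3.4% change in radius failure load". For 35 pairs the 80%-power effect is 0.4875 SD of change, and power at 0.5 SD is 82.0%. Taking 7.0% as the SD of change, 0.4875 × 7.0% = 3.41%, which is the stated 3.4%. Where it can be checked in percentage units, then, the sample-size section uses the SD of change.

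**The case against.** The best defence is that 0.91 was meant in between-patient SDs. Aim 3, in the same section, gives this some support. Its SD comes from a cohort study of T50 levels and mortality, which reads as an SD of level, and it says 35 patients can detect 0.7 SD. On the SD-of-change scale 35 pairs detect 0.49 SD. On the between-patient scale with r = 0 they detect 0.4875 × √2 = 0.689, which rounds to 0.7. The sample-size section may therefore not use one scale throughout, and Aim 2 alone does not settle what Aim 1 meant.

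This stands as a reason to make the correction conditional, but it does not rescue the figure. On the same convention (r = 0), Aim 1 would read 0.934, not 0.91. A two-sample formula fits both figures: 0.909 for 20 per group and 0.679 for 35 per group. And the between-patient reading still needs an r that is nowhere stated.

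A correlation near zero is hard to square with a change expected to be similar across patients, but it is not excluded. That expectation concerns the treatment effect. The SD of the observed change also contains measurement noise, here from averaging a limited number of readings in differently labelled regions: "A total of 12-15 indentations will be performed within a given region".

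Two further objections are fair. First, 0.66 SD assumes that all 20 pairs are evaluable. No attrition allowance is stated and missing outcomes will not be imputed; with an assumed 18, 16 or 14 pairs the 80%-power effect is 0.70, 0.75 or 0.81 SD of change. Second, once there are data, the confidence interval for the change in hardness will matter more than a planning figure. That limits the weight of the point.

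**Conclusion.** The concern holds, as a minor point. The SD is undefined, and the stated figure is not what the stated paired test gives on its natural scale. That result is exact for 20 evaluable pairs and approximately normal changes. The between-patient reading brings power to 80% only at r of about 0.05; at r = 0 it falls slightly short, and at larger r it is well above.

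The two-sample origin is an inference, and the conclusion does not depend on it. On the SD-of-change reading the misstatement is conservative: the sample size is not called into question, and there is room to lose biopsies before power for 0.91 SD drops below 80%.

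**What to change.** Reword the effect-size sentence in the Aim 1 sample-size paragraph to say that 20 evaluable patients give 80% power for a mean within-patient change of 0.66 SD of the change, and 97% power for 0.91 SD.

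If the between-patient SD of hardness was intended, say so instead, give the assumed pre/post correlation, and reconcile it with the sentence that expects a similar change across patients. The sponsor should confirm which SD was meant before the number is replaced.

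The cost is one sentence. The sample size, the test, the procedures and the Aim 2 and Aim 3 paragraphs need no change for this point.
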